#### **4.4.4. Handling of missing values and early dropouts in the efficacy analyses during the study period as a whole (full 24 weeks)**

This is for the “efficacy chapter 2” analysis.

For binary data (e.g., ACR20), two different imputations will be done for missing visits as well as early dropouts: non-responder imputation (NRI) and LOCF, up to and including Week 24. The NRI imputation will be primary, and LOCF will be secondary.

For other data (ordinal or continuous), missing visits as well as early dropouts will be imputed using the last observation carried forward (LOCF) algorithm, up to and including Week 24.

For all parameters, an observed-case analysis will also be performed (i.e., without any imputation). This observed-case will not be shown for subjects who switched treatment. See previous section for the parts where the observed-case analysis will be presented.

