Consequently, each subject will remain in the study for a maximum of 29 weeks (from Screening visit to Follow-up visit).

A diagram of the study design can be found below.

| Week 1 - 12                | Week 13 – 24   |
|----------------------------|--|
| Randomized to placebo      | Responders (i.e., having at least 20% improvement on TJC68 and SJC66) remain on placebo |
|                            | Nonresponders re-randomized to 100 mg q.d.   |
|                            | Nonresponders re-randomized to 50 mg b.i.d.  |
| Randomized to 50 mg q.d.   | Responders remain on 50 mg q.d.   |
|                            | Nonresponders assigned to 100 mg q.d.   |
| Randomized to 25 mg b.i.d. | Responders remain on 25 mg b.i.d.   |
|                            | Nonresponders assigned to 50 mg b.i.d.  |
| Randomized to 100 mg q.d.  | Remain on 100 mg q.d.   |
| Randomized to 50 mg b.i.d. | Remain on 50 mg b.i.d.  |
| Randomized to 200 mg q.d.* | Remain on 200 mg q.d.*  |
| Randomized to 100 mg b.id* | Remain on 100 mg b.i.d.*  |

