## 1.2. STUDY DESIGN

This is a multicenter, phase IIb, double-blind, placebo-controlled add on study in subjects with moderately to severely active RA who have an inadequate response to MTX. A total of 595 subjects will be randomized to one of 6 dose regimens of GLPG0634 or to placebo, on top of their stable dose of MTX. Treatment duration will be 24 weeks. At Week 12, subjects on placebo who have not achieved a 20% improvement in swollen joint count (SJC66) and tender joint count (TJC68) will be re-randomized (automatically via interactive voice/web response [IXRS]) to treatment to receive GLPG0634 100 mg q.d. or 50 mg b.i.d. doses in a blinded fashion, subjects on 50 mg q.d. who have not achieved a 20% improvement in SJC66 and TJC68 will be assigned to 100 mg q.d. and subjects on 25 mg b.i.d. who have not achieved a 20% improvement in SJC66 and TJC68 will be assigned to 50 mg b.i.d. All will continue the study until Week 24. Subjects in the other treatment groups will maintain their randomized treatment until Week 24.

Upon qualification for the study, subjects will be randomized to placebo or one of 6 dosing regimens in a 1:1:1:1:1:1 ratio (N=85 for each treatment group; total N=595), stratified by geographic region and previous use of a biological DMARD during a single clinical study setting.

[figure not shown]
Subjects participating in the study will be requested to attend a maximum of 11 visits throughout the study: Screening visit (up to 28 days before Baseline visit), Baseline visit, Week 1 visit, Week 2 visit, Week 4 visit, Week 8 visit, Week 12 visit, Week 16 visit, Week 20 visit, Week 24 visit (and potentially a follow-up visit). At completion of the 24-week

treatment period, subjects will be offered the option to enter a Long Term Follow-up study (GLPG0634-CL-205). For the subjects not entering the GLPG0634-CL-205, an additional final Follow-up visit will be scheduled 7 to 10 days after end of study treatment.

Consequently, each subject will remain in the study for a maximum of 29 weeks (from Screening visit to Follow-up visit).

Data from the Long Term Follow-up study 205 will be presented in a separate analysis, and is not part of this SAP.

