## **4.2. CALCULATION OF PERCENTAGES**

Missing values will not be included in the denominator count when computing percentages.

Imputed missing values are no longer considered to be missing values.

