### **4.4.3. Handling of missing values and early dropouts in the efficacy analyses during the first study period (up to Week 12)**

This is for the “efficacy chapter 2” analysis.

For binary data (e.g., ACR20), two different imputations will be done for missing visits as well as early dropouts: non-responder imputation (NRI) and LOCF, up to and including Week 12. The NRI imputation will be primary, and LOCF will be secondary.

For other data (ordinal or continuous), missing visits as well as early dropouts will be imputed using the last observation carried forward (LOCF) algorithm, up to and including Week 12.

Definitions of the imputation methods:

- LOCF (all types of parameters, from binary to continuous): to impute a missing value, the last preceding nonmissing value will be used (which could even be a baseline value).
- NRI (binary response parameters only): to impute a missing response, the subject will be assumed to be a non-responder.

For all parameters, an observed-case analysis will also be performed (i.e., without any imputation). The observed-case analysis will serve as a sensitivity analysis (to ascertain the impact of early dropouts on the results) and will basically be limited to:

- ACR20/50/70/N: descriptive at W12+W24 and inferential at W12
- EULAR remission: descriptive at W12+W24
- SDAI/CDAI: descriptive at BSL+W12+W24
- DAS28: descriptive at BSL+W12+W24 and inferential at W12
- All ACR components (VAS, joint counts, CRP, HAQ-DI): descriptive at BSL+W12+W24
- QoL (FACIT,SF-36): descriptive at BSL+W12+W24.

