#### **4.5.1. In the efficacy analysis of the full study as a whole (full 24 weeks)**

The efficacy analysis will apply the original 7 treatment groups (original randomization at baseline). Subjects who switch treatment at Week 12 will be regarded as having discontinued treatment at Week 12: their data after Week 12 will not be used in this analysis. Their efficacy data will be handled for the remainder of the study as described above in section 4.4.4. The placebo, 50 mg q.d. and 25 mg b.i.d. groups will thus contain both data under this treatment (continued treatment groups), as well as Week 12 imputed information from non-responders who switch to a higher dose of GLPG0634. It is recognized that these 3 groups (placebo, 50 mg q.d. and 25 mg b.i.d.) will only be an approximation, so the formal comparisons between all groups after Week 12 should be interpreted with care. LOCF, NRI and observed-case will be produced.

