#### **Table 14.2.1.1.1: ACR20: Summary with overall p-value and pairwise comparisons versus placebo**

Logistic regression model at each time point, modeling the responders. Factors in the model are: treatment, region, and previous use of biologics.

Per time point, the table will present:

- Overall type-III p-value for all explanatory factors in the model.
- Per group: number and percentage of responders, difference in percentage responders versus the placebo group (GLPG0634 minus placebo), together with a 95% confidence interval of this difference (as provided by SAS PROC FREQ).
- Per group: p-value for pairwise comparison versus the placebo group, derived from contrasts within the overall regression model. These p-values will be presented both as uncorrected p-values as well as corrected for multiplicity according to Hommel's closed-testing method (SAS PROC MULTTEST).

The "raw" SAS PROC output must be provided in a statistical appendix listing.

The table will show:

- NRI in ITT and in per-protocol
- LOCF in ITT and in per-protocol
- observed-case in ITT (descriptive at Week 12 + 24; inferential statistics at Week 12 only).

Table to be created for the Week 12 interim analysis as well, cut off at Week 12. ITT only.

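### The Week 24 observed-case tables by original arm keep only Week 12 joint-count responders in placebo and the two 50 mg/day arms, but all remaining subjects in the 100 and 200 mg/day arms

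*SAP*

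**What the plan says.** SAP 2.1.1 calls the analysis of the seven original arms over 24 weeks Chapter 2. SAP 1.2 sets the switch rule. It covers, in its words, "At Week 12, subjects on placebo who have not achieved a 20% improvement in swollen joint count (SJC66) and tender joint count (TJC68"), who are re-randomized to 100 mg q.d. or 50 mg b.i.d. It also says that "subjects on 50 mg q.d. who have not achieved a 20% improvement in SJC66 and TJC68 will be assigned to 100 mg q.d", and treats 25 mg b.i.d. in the same way with a move to 50 mg b.i.d. The other four arms keep their randomized treatment whatever their Week 12 result. The diagram in Protocol 8.1 defines those who stay on placebo by joint counts alone: "Responders (i.e., having at least 20% improvement on TJC68 and SJC66").

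For switchers in Chapter 2, SAP 4.5.1 says "their data after Week 12 will not be used in this analysis", and 4.4.4 adds "This observed-case will not be shown for subjects who switched treatment". SAP 4.2 fixes the denominator: "Missing values will not be included in the denominator count when computing percentages".

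SAP 4.4.3 gives the purpose: "The observed-case analysis will serve as a sensitivity analysis (to ascertain the impact of early dropouts on the results"). It lists Week 24 observed-case output for ACR20/50/70/N, remission, SDAI/CDAI, DAS28, the ACR components, FACIT and SF-36. The ACR20 table definition (Table 14.2.1.1.1) reads "observed-case in ITT (descriptive at Week 12 + 24; inferential statistics at Week 12 only").

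**The concern.** Three of the seven columns are selected on a Week 12 outcome and the other four are not, yet all seven stand side by side under the original randomized labels. If Week 12 response predicts Week 24 response at all, the three selected columns are pushed upward.

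Two things are at stake. First, the stated purpose fails at Week 24: most of the subjects missing from the placebo column would be switchers, not early dropouts. Second, the apparent dose-response is distorted. Placebo and the 50 mg/day arms look closer to the 100 and 200 mg/day arms than they are, and could look better.

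**Working it through.** **Inputs from the documents.** Protocol 8.8.2 gives 85 subjects per arm, alpha 5%/6 per comparison, placebo ACR20 of 20-40% at Week 12, and active rates of 48% (against 20%) and 70% (against 40%) at 90% power, or 45% and 66% at 80% power.

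**The plan's own figures.** Pooled chi-square power, taken as two-sided: Φ([|p1−p0|√n − z√(2p̄(1−p̄))] / √(p0(1−p0)+p1(1−p1))). For 48% against 20%, z = 2.638 and p̄ = 0.34, so (0.28×9.220 − 2.638×0.670)/0.640 = 1.27, a power of 90%. The other pairs give 91% (70 vs 40), 81% (45 vs 20) and 78% (66 vs 40). The stated figures reproduce to within 2 points, so these rates are used below.

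**Assumptions, because the documents are silent.** Let p be placebo ACR20 at Week 12 and e the share who meet the joint-count rule but not ACR20 (these subjects stay). Then j = p + e is the share kept. I take e = 10 points and no early dropout. The 100 and 200 mg/day columns keep everyone, so I hold them at the design rate.

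**Step 1, who is left.** At p = 20%, j = 30%: 85×0.30 ≈ 26 placebo subjects kept and 59 removed. At p = 40%, j = 50%: 85×0.50 ≈ 42-43 kept and about as many removed.

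**Step 2, bias with imperfect persistence.** Take a bivariate normal latent response with correlation ρ between Week 12 and Week 24 and an unchanged true rate p. The column shows P(ACR20 at Week 24 | joint-count response at Week 12).

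| True placebo rate | ρ = 0.5 | ρ = 0.7 | ρ = 0.9 | Bias | Design active rate |
|---|---|---|---|---|---|
| 20% | 38% | 48% | 60% | 18-40 points | 48% |
| 30% | 48% | 57% | 68% | 18-38 points | – |
| 40% | 56% | 64% | 74% | 16-34 points | 70% |

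Varying e from 5 to 20 points widens the bias range to 13-47 points.

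**Step 3, can the order reverse?** Let s be the share of ACR20 responders who still respond at Week 24, and g the share of the e group who gain response. The placebo column shows (p·s + e·g)/(p + e).

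- s = 1, g = 0: 0.20/0.30 = 66.7% against 48%; 0.40/0.50 = 80.0% against 70%. Reversed.
- s = 0.8, g = 0.2: (0.16+0.02)/0.30 = 60.0% against 48%, reversed; (0.32+0.02)/0.50 = 68.0% against 70%, nearly equal.
- s = 0.6, g = 0.1: (0.12+0.01)/0.30 = 43.3% against 48%; (0.24+0.01)/0.50 = 50.0% against 70%. Not reversed, but true gaps of 28 and 30 points shrink to about 5 and 20.

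With constant status, placebo equals or beats active when j is at most p divided by the active rate: 0.20/0.48 = 41.7%, or 0.40/0.70 = 57.1%.

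**Step 4, the 50 mg/day columns.** They are filtered in the same way. Suppose such an arm truly matched the higher doses at 48%. With e = 10 points and constant status it would show 0.48/0.58 = 82.8% beside their 48%.

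**The case against.** The strongest reply is that little rests on these cells. Week 24 observed-case is descriptive, limited to the ITT population, and has no plots and no p-values. The primary endpoint is Week 12 ACR20 with NRI. At Week 24, NRI is primary and LOCF secondary for binary data. The documented input to dose selection is the interim analysis, which is cut off at Week 12. The reduced counts would be visible in the tables. All of this stands, and it limits the weight of the point. A reader might infer that the primary result or the dose choice is compromised; the documents do not support that.

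The second reply is that the SAP already deals with the matter. Chapter 3 shows Week 12 responders in seven continued arms and non-responders in eight others, with observed-case results at Weeks 12 and 24. This also stands, and it supplies the fix. SAP 4.5.1 does warn that the three groups are only approximate after Week 12. However, that caution concerns formal comparisons and imputed Week 12 data. It does not tell the reader that the observed-case columns contain responders only.

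The third reply is that the inputs are assumed and a reversal is not assured. This is correct. The 10-point joint-count gap, the correlations and the values of s and g are not in the documents. Against the design rates, the latent model gives a clear reversal only at ρ = 0.9 and a tie at ρ = 0.7 in the 20% case. The direction of the bias needs only that Week 12 response predicts Week 24 response.

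**Conclusion.** The point holds for the Chapter 2 Week 24 observed-case tables only. The placebo, 50 mg q.d. and 25 mg b.i.d. columns are selected on Week 12 joint-count response and are biased upward. For placebo ACR20 the bias is about 16-40 points, if joint-count response is 10 points above a 20-40% ACR20 rate and the latent correlation is 0.5-0.9. The difference from the 100 and 200 mg/day arms shrinks, and reverses only if response persists strongly. At Week 24 the table cannot gauge early dropout.

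Two stronger readings should be avoided. One is that every ACR20 non-responder is removed. The rule uses joint counts, so subjects who meet it but miss ACR20 stay. Under SAP 2.4.1, the rare subject known to have taken no drug after Week 12 has the re-randomization ignored. The other is that placebo will look better than active drug. It can, but the documents do not establish that it will.

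The Week 12 primary analysis, the Week 12 observed-case tests and the Week 24 NRI and LOCF tables are not affected by this exclusion.

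**What to change.** In SAP 4.4.3, 4.4.4 and the affected table definitions, do not present Chapter 2 Week 24 observed-case results for placebo, 50 mg q.d. and 25 mg b.i.d., or drop Week 24 from the Chapter 2 observed-case output altogether. Refer instead to the Chapter 3 observed-case tables. Bring SAP 4.5.1, 6.1.2.3 and the general comments in section 8 into line, since they promise observed-case output without this limit. Leave Week 12 observed-case unchanged.

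If the three columns are kept, label them *Week 12 joint-count responders only* and state that they are not comparable with the 100 and 200 mg/day columns.

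Do not pool post-switch data under the original arm in this table. That would contradict SAP 4.5.1 and 6.1.2.3, and it replaces selection with contamination. Suppose stayers keep their status and switchers respond at the design active rates (an assumption). Placebo would then show 0.20 + 0.70×0.48 = 54% against 48%, or 0.40 + 0.50×0.70 = 75% against 70%.

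The cost is SAP wording and a table filter. The downside is that Week 24 observed-case results for the three arms appear only in Chapter 3.

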#### **4.4.5. Handling of missing values and early dropouts in the efficacy analyses during the second study period (after Week 12)**

This is for the “efficacy chapter 3” analysis.

Subjects in this analysis must have data after the Week 12 potential switch in dosing. Subjects who discontinued the study during the first period of the study will not be included in this analysis and will therefore also not be imputed.

For binary data (e.g., ACR20), two different imputations will be done for missing visits as well as early dropouts during period 2: non-responder imputation (NRI) and LOCF, up to and including Week 24. The NRI imputation will be primary, and LOCF will be secondary.

For other data (ordinal or continuous), missing visits as well as early dropouts during period 2 will be imputed using the last observation carried forward (LOCF) algorithm, up to and including Week 24.

Note that no Period 1 efficacy data will be carried forward into this chapter 3 analysis.

For all parameters, an observed-case analysis will also be performed (i.e., without any imputation).

#### **4.4.6. Handling of missing values and early dropouts in the safety analysis**

No imputation is done of missing values or missing visits. The analysis will be observed-case only.

### **4.5. HANDLING TREATMENT SWITCHES AT WEEK 12 IN THE EFFICACY AND SAFETY ANALYSIS**

This section only applies to the Week 12 non-responders in the placebo and low dose groups, where there is a dose increase for the remaining 12 weeks until the end of the study, and also to the Week 12 responders in the placebo and low dose groups, who remain on the same treatment for the remaining 12 weeks until the end of the study.

#### **4.5.1. In the efficacy analysis of the full study as a whole (full 24 weeks)**

The efficacy analysis will apply the original 7 treatment groups (original randomization at baseline). Subjects who switch treatment at Week 12 will be regarded as having discontinued treatment at Week 12: their data after Week 12 will not be used in this analysis. Their efficacy data will be handled for the remainder of the study as described above in section 4.4.4. The placebo, 50 mg q.d. and 25 mg b.i.d. groups will thus contain both data under this treatment (continued treatment groups), as well as Week 12 imputed information from non-responders who switch to a higher dose of GLPG0634. It is recognized that these 3 groups (placebo, 50 mg q.d. and 25 mg b.i.d.) will only be an approximation, so the formal comparisons between all groups after Week 12 should be interpreted with care. LOCF, NRI and observed-case will be produced.

#### **4.5.2. In the safety analysis of the full study as a whole (full 24 weeks)**

The treatment groups that will be presented in the tables will distinguish treatment switches at Week 12 as separate arms: the period 1 & 2 treatment sequence will be used.

#### **4.5.3. In the efficacy and safety analysis of the second study period**

The treatment arms will be presented descriptively only, as separate columns.

In the safety analysis, this only applies to the adverse events where the treatment-emergent AEs that emerge during the second part of the study will be presented separately. The lab data, ECG and vital signs are already presented in chapter 2 of the analysis.

#### **4.6. HANDLING OF OUTLIERS**

All measured values will be included in the analyses.

#### **4.7. HANDLING OF SECONDS IN DATETIME FIELDS**

If a datetime field contains seconds, these will be cut off (i.e., rounded down to the minute) prior to data analysis. The analysis will only use the date and time up to the minute.

#### **4.8. STRATIFICATION FACTORS**

In case there is a discrepancy in randomization stratification stratum between IWRS and the actual eCRF data, then:

1. The actual eCRF stratum will be used in analyses and analysis models, and
2. Any such discrepancy will be flagged in the listing on randomizations (listing 16.2.1.1).

### **5. SOFTWARE AND PROCEDURES**

#### **5.1. SOFTWARE**

SAS version 9.3 (or higher) will be used for programming.

#### **5.2. PROCEDURES**

Analyses will comply with ICH regulations, in particular: (ICH-E3) , (ICH-E6) and (ICH-E9).

The following Galapagos SOPs will be followed:

- SOP-CLI-001: Developing Clinical Study Documents (version 1.0)
- SOP-CLI-003: Managing Data Processing Activities (version 1.0)
- SOP-CLI-004: Managing DSMB Activities (version 1.0)

The following ████ STAT SOPs will be followed:

Location	Document Type	Document Number	Effective Date	Document Title
Global	SOP	03.002.01	03-Feb-2014	Providing Statistical Input to CSRs and Clinical Summaries for Submission Dossiers
Global	SOP	03.003.00	06-Feb-2012	Generation of define.xml
Global	SOP	03.004.01	03-Feb-2014	Statistical Input to Clinical Trial Protocols
Global	SOP	03.005.00	29-Mar-2012	Planning and Conducting Interim Analyses
Global	SOP	03.007.01	01-Oct-2013	Development of a Statistical Analysis Plan
Global	SOP	03.009.01	01-Oct-2013	Quality Control of SAS® Programming
Global	SOP	03.010.01	01-Oct-2013	Development of SAS® Programs
Global	SOP	03.011.00	30-Apr-2012	Randomization and Unblinding
Global	SOP	03.012.02	02-Dec-2013	Biostatistics and Statistical Programming Directory Structure Creation and Setup
Global	SOP	03.013.01	01-Oct-2013	Development and Production of Analysis Datasets
Global	SOP	03.014.01	29-Apr-2014	Biostatistics and Statistical Programming Functional Lead Responsibilities
Global	SOP	03.015.01	29-Apr-2014	Performing Blind Review of Data

### **5.3. FORMATS**

Derived data will be following CDISC ADaM 2.1 (ADaMIG 1.0) format.

Tables, listings and figures will follow the Mock TLFs, as provided in a separate document.

## **6. STATISTICAL METHODS**

### **6.1. PLANNED ANALYSES, PROTOCOL AMENDMENTS INCLUDED**

#### **6.1.1. Demographic and other baseline characteristics**

Subject disposition including the reasons for study termination will be tabulated.

Demographic characteristics will be listed. Demographic characteristics will be summarized using appropriate descriptive statistics, as applicable.

## 6.1.2. Efficacy Variables

### 6.1.2.1. Definition of primary efficacy endpoint: ACR20 at Week 12

The primary endpoint is the percentage of subjects achieving an ACR20 response at Week 12. Other time points will be regarded as secondary endpoints. The non-responder imputation (NRI) of the ACR20 will be the primary parameter, with observed-case and last observation carried forward (LOCF) imputation as secondary confirmatory analyses.

The ACR response is a measurement of improvement in multiple disease assessment criteria. The ACR20 response is defined as:

≥20% improvement from baseline in SJC66 (66 joints) and TJC68 (68 joints)

AND

≥20% improvement from baseline in at least 3 of the following 5 assessments

- Pain (VAS) in cm (from HAQ-DI).
- Patient's Global Assessment of Disease Activity (VAS) in cm.
- Physician's Global Assessment of Disease Activity (VAS) in cm.
- Patient's Assessment of Physical Function as measured by HAQ-DI.
- CRP in mg/L.

